5.1.12. Randomization

Upon enrolment to the study, subjects will be randomized 1:1 to a study arm or to a control arm. The randomization process will adopt a blocked randomization strategy, using pre-defined random block sizes of 2 and 4. Each investigational site will be provided with a set of envelopes with randomization assignments. Randomization envelopes are labelled with a unique envelope number and are to be opened in consecutive order.

5.2. Treatment visits

The schedule of treatments includes 4 treatments, at intervals of 2 weeks. The subject can advance the next treatment session by up to 3 days, or delay it by up to 7 days. The first treatment may occur on the same day as the screening visit, or up to 1 week from the screen visit. Each treatment session will include an IPL treatment or a sham IPL treatment, followed by MGX.

5.2.1. Pre-Treatment Procedures

- Before treatment, the subject's face must be thoroughly cleaned with a mild cleansing agent, like soap, facial wipes, or a medical grade alcohol diluted by 50%.
- The area to be treated will be coated with a thin (1-2 mm) layer of transparent coupling gel (provided by Lumenis).
- Both eyes of the subject must be completely occluded with protective goggles. The goggles must cover the entire peri-ocular region, including the upper and lower eyelids.
- In all subjects, several test spots (active IPL or sham IPL, depending on the arm) will be given in inconspicuous areas of the facial skin, for example on the lateral aspect of the malar region. In subjects of the control arm, these sham spot tests will have no function other than to mimic the actual treatment. In subjects of the study arm, these test spots will be used to determine the IPL settings.
- For the first treatment session, the IPL settings for the 1st test spot may be set using the values recommended in Table 2, or using less intensive settings at the discretion of the investigator(s). For subsequent treatment session, the IPL settings for the 1st test spot may be copied from the IPL settings used in the previous treatment session, unless the long-term skin reaction is not acceptable (including: a break in skin integrity, blistering, sloughing and/or discoloration or bruising). In this latter case the intensity of IPL settings for the 1st test spot should be reduced with respect to IPL settings used in the previous IPL session, either by decreasing the fluence, increasing the pulse duration, and/or increasing the delay.
- After each test spot, the investigator will wait a few minutes and then will examine the immediate skin reaction. If the skin reaction is acceptable and as expected (pinkish to red appearance of the skin, which should gradually fade within a few minutes), the IPL treatment
 QF-1044440 Rev. D Global Clinical Study Report Template GEN-0010523 Effective Date: July-2017

U Lumenis [®] Energy to Healthcare	
Description: LUM-VBU-M22-IPL-17-01_Protocol - Clinical s protocol for M22 Dry Eye	tudy

itself can continue with these settings. If the skin reaction is excessive (including: a break in skin integrity, blistering, sloughing and/or discoloration or bruising), or if the subject complains of more than mild pain/discomfort, the intensity of the IPL will be reduced either by decreasing the fluence, increasing the pulse duration and/or increasing the delay. Then, a new test spot will be performed.

- Up to 5 test spots are recommended. If the immediate skin reaction after these test spots is not acceptable (including: a break in skin integrity, blistering, sloughing and/or discoloration or bruising), upon decision of the investigator this subject may be discontinued from the study. It is recommended to perform up to 5 test spots.
- Whether or not the IPL settings were modified from the previous treatment session, the IPL settings used for the current treatment must be recorded in the appropriate eCRF.

5.2.2. Treatment

- IPL pulses will be administered on the entire malar region, below the lower eyelids, from tragus to tragus including the nose. Adjacent pulses should be given with overlaps of about 1 mm.
- In subjects with skin type I-III, two passes will be performed. The first pass will be performed in one orientation of the IPL lightguide (for example, when the long side of the lightguide is parallel to the nose axis), and the second pass will be performed in the perpendicular orientation (in this example, when the short side of the lightguide is parallel to the nose axis). In subjects with skin type IV, a single pass or a double pass will be performed, at the discretion of the study investigator.
- If needed, the lightguide can be changed from small to large, for better accessibility.
- In subjects of the control arm, the IPL treatment will be sham. The study investigator will touch
 the skin with the lightguide of the IPL handpiece, as he/she would have done if the subject was
 in the study arm, but the trigger button will not be pressed. A clicking sound will be played
 whenever the sapphire lightguide will touch a new location on the skin, to give the subject the
 impression that the treatment is given.
- At the end of the IPL or sham treatment, the protective goggles will be removed.
- The subject will then assess his/her own level of pain/discomfort using a Visual Analog Scale (VAS).
- Then, each eye will be numbed with a topical solution, for example Proparacaine Hydrochloride 0.5%, and the meibomian glands of both the upper and lower eyelids will be manually expressed. Expression of the meibomian glands will be done by squeezing the meibomian glands with the aid of two Q-tips positioned on either side of the meibomian glands, or with a meibomian gland expressor forceps. Upon decision of the study investigator, the Q-tips or the meibomian gland expressor forceps may be dipped in a numbing solution as well. Squeezing the

QF-1044440 Rev. D Global Clinical Study Report Template GEN-0010523	Effective Date: July-2017
---	---------------------------

glands will be performed for 8 seconds or as soon as the glands are expressed, whichever comes first.

- Following MGX, the subject will assess his/her own level of pain/discomfort using a Visual Analog Scale (VAS).
- Up to 10 minutes later, the study investigator will assess the immediate/short term response (erythema, edema, purpura, etc.) of the skin using a 5 level scale: 0 = None, 1 = Trace, 2 = Mild, 3= Moderate; 4 = Severe.
- Longer term response (e.g. dryness) of the skin are anticipated to appear after the treatment and should disappear within several days. This will be documented in a specific section of the electronic Case Report Form (eCRF), at the next visit.

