The recommended IPL settings are the numbers to the right of the inequality signs for fluence, pulse duration and pulse delay. For filters, it is recommended to use the values not in parentheses. These values are recommended but can be modified, at the discretion of the investigator. *: Only for subjects in the study arm. For subjects in the control arm, use a filter which blocks all wavelengths. This filter is labeled with a red sticker and the symbol " ∞ ".

Skin type	Fluence (J/cm ²)	Filter (nm) *	Pulse structure	Pulse duration (msec)	Delay (msec)	Chiller
I	≤ 20	560 (or 590)	Triple	≥ 3	≥ 15	On
II	≤ 19	560 (or 590)	Triple	≥ 3.5	≥ 20	On
III	≤ 18	560 (or 590)	Triple	≥ 3	≥ 25	On
IV	≤ 17	590	Triple	≥ 3	≥ 30	On

THIS SPACE INTENTIONALLY LEFT BLANK

Revision: C State: Released ECO No: ca-00000172 Effective Date: 19-Sep-2019

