2.6. Comparator device (control arm)

Subjects in the control arm will undergo exactly the same procedures as subjects in the study arm (section 2.5), except that IPL treatment will be sham. The sham IPL treatment will be implemented by blocking all wavelengths emitted by the Xenon flash lamp, using the ∞ filter (see section 2.1.3).

QF-1044440 Rev. D	Global Clinical Study Report Template	GEN-0010523	Effective Date: July-2017

3. Study Design

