3.1.1. Randomization

Upon enrollment to the study, subjects will be randomized 1:1 to a study arm or to a control arm. The randomization process will adopt a blocked randomization strategy, using random block size of 2 and 4. Each investigational site will be provided with a set of envelopes with randomization assignments. Randomization envelopes are labeled with a unique envelope number and are to be opened in consecutive order.

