3.8. Concurrent Control

Subjects will be randomized 1:1 to a study arm and to a control arm. Subjects in the control arm will undergo exactly the same procedures as subjects in the study arm, with the exception that the IPL pulses will not be actually delivered. This applies to both test spots and the full treatment.

Due to the nature of the IPL treatment, it is not possible to ensure masking of the subjects, as subjects are generally aware that IPL treatment should be felt and should normally leave a temporary redness of the skin. This said, the following steps will be taken:

In the informed consent process, subjects will be told that in some cases the IPL treatment might be felt as a mild pain/discomfort on the skin, and that the treatment can cause redness of the skin that should disappear within a few minutes. During IPL administration, all subjects will wear protective goggles that will completely occlude their vision.

In the control arm, subjects will undergo a sham treatment that will mimic the IPL (IPL) therapy. The sham treatment will be implemented using a filter that blocks all light emitted by the M22-IPL (the ∞ filter described in section 2.1.3). The tip of the lightguide will still be cooled and the device will still produce clicking sounds whenever the trigger button on the IPL handpiece is triggered, but no light will be actually transmitted to the skin. Following the sham IPL procedure, subjects will undergo meibomian gland expression.

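### Optional tool numbing at gland expression is decided by a role that can tell the arm, and could partly hide the expected MGX-pain benefit

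*Protocol*

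**What the plan says.** **The MGX step.** Protocol 5.2.2 places MGX after IPL or sham in each of the four sessions. It requires that "each eye will be numbed with a topical solution, for example Proparacaine Hydrochloride 0.5" per cent, in both arms. Expression is then done "with the aid of two Q-tips positioned on either side of the meibomian glands, or with a meibomian gland expressor forceps", with no rule for choosing between the two. Numbing of the tool itself is optional: "Upon decision of the study investigator, the Q-tips or the meibomian gland expressor forceps may be dipped in a numbing solution as well".

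**Parity between arms.** Section 2.6 gives control subjects "exactly the same procedures as subjects in the study arm (section 2.5), except that IPL treatment will be sham". Section 2.5 covers only the administration of IPL pulses and contains no MGX step. Section 3.8 is broader and gives control subjects "exactly the same procedures as subjects in the study arm, with the exception that the IPL pulses will not be actually delivered".

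**Who knows the arm.** The note to Table 2 says of the sham filter: "This filter is labeled with a red sticker". In 5.2.2 the study investigator handles the sham as for active treatment, "but the trigger button will not be pressed". The masking steps in 3.9 concern the examiner at baseline and follow-up.

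**The endpoint.** MGX pain or discomfort, self-rated on a VAS, is a between-arm safety endpoint (Protocol 3.5.5, SAP 2.5). Section 1.2 expects less of it with IPL. SAP 5.6.1 tabulates pain by visit and group, and 5.6.3 summarises the safety endpoints by group. Neither plans to show the tool or the tool numbing used.

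**The concern.** A pain comparison is easiest to read when pain relief is given alike in both arms. Here the basic numbing is mandatory, but the extra numbing is discretionary. The decision is made after randomisation by a role that can tell which treatment has just been given.

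The protocol itself supplies a route to unequal use, and it needs no bad intent. If sham subjects have thicker meibum and a more uncomfortable expression, a considerate operator has more reason to dip the tool for them. The sham arm would then score lower than it would under equal numbing, and the IPL advantage expected in 1.2 would look smaller. A reader of the planned tables could not separate a small true benefit from a larger one that extra numbing had partly masked.

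**Working it through.** The documents give no effect size, SD or power for MGX pain, so there is no plan figure to reproduce. The main check is of the text.

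1. **Is the step optional and open?** Yes. Section 5.2.2 gives no criterion for dipping and does not require the choice to match across arms or sessions. The tool choice is equally open.
2. **Does a parity rule settle it?** Only in part. Section 2.6 refers to 2.5, which has no MGX step, so parity for MGX rests on 3.8. That section makes the same option available to both arms. Dipping more often in one arm than the other would not breach it.
3. **Is the arm known when the choice is made?** The study investigator delivers IPL or sham, and the same role decides on dipping. Either the marked filter or the unpressed trigger reveals the arm.
4. **Is there a documented reason for use to differ?** Section 1.1.2 says expression is more uncomfortable when meibum is viscous. Section 1.2 says IPL heat may liquefy meibum and ease expression. Together they point to more reason for extra numbing in the sham arm.
5. **Which way would that push the result?** Lower sham pain scores mean a smaller apparent benefit of IPL.

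**Illustration of size, for tool numbing only.** The effect, the difference in use, the SD and the 0–100 pain scale are all assumed. The 83 completers come from Protocol 7.3.2, split here as 41 and 42.

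- Shift = (VAS reduction from tool numbing) × (difference between arms in the proportion receiving it).
- Low end: 2 × 0.10 = 0.2 points. High end: 10 × 0.40 = 4 points.
- The assumed differences in use correspond to about 0.10 × 41 = 4.1 to 0.40 × 42 = 16.8 subjects in an arm.
- 95% CI half-width at one visit = t(0.975, 81 df) × SD × √(1/41 + 1/42) = 1.990 × SD × 0.2195. SD 20 gives 8.74, SD 25 gives 10.92 and SD 30 gives 13.10.
- The largest shift relative to these half-widths is 4/8.74 = 0.46 at SD 20 and 4/13.10 = 0.31 at SD 30.

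Under these assumptions the shift stays below half of a single-visit CI half-width. With equal use in both arms it is zero.

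**The case against.** The strongest case against is that most of MGX is already standardised and the endpoint is minor.

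- **Standardisation.** Every eye is numbed, upper and lower lids are expressed in both arms, and squeezing stops at 8 seconds or on expression. This stands. It leaves less room for extra numbing to matter.
- **Site habit.** Each site has its own envelopes, with blocks of 2 and 4, and "Randomization envelopes are labeled with a unique envelope number and are to be opened in consecutive order". A fixed site practice would be roughly balanced between arms. This also stands: only a choice that varies with the arm can distort the comparison.
- **A consequence of treatment.** If extra numbing follows from thicker meibum, a comparison with numbing as needed is legitimate. That is fair, but it answers a different question from pain under equal numbing. The reader needs the numbing data to know which question was answered.
- **Inference.** No sentence says operators adjust numbing to viscosity, or that one person both treats and expresses. The point is therefore a possibility and not a finding of bias.
- **A larger limit.** Section 3.8 concedes that subject masking cannot be ensured, and MGX pain is self-rated. Expectation effects would remain after any change made here.
- **Low stakes.** MGX pain is one of six safety endpoints. SAP 5.6 plans only description of it, with no stated test or decision rule.

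These arguments set the priority low. They do not close the gap, because none of them equalises use of the optional step.

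**Conclusion.** The point holds as a minor design improvement. A role that can tell the arm may add pain relief just before a self-rated pain endpoint is measured, and the general parity rule does not control how often. The direction with support in the documents is masking: more numbing in sham subjects, partly hiding the benefit expected in 1.2. The size is unknown, and the 0.2 to 4 points is only an illustration. The conclusion rests on two assumptions: that numbing the tool adds something beyond the drops, and that its use varies with the arm.

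A reader might infer more than the documents support:

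- **No parity rule exists.** Section 3.8 is one. It simply does not govern the frequency of an optional step.
- **The IPL pain benefit would be exaggerated.** This would need more numbing in active subjects, for which the documents give no mechanism.
- **Tool choice distorts pain.** Nothing in the documents says Q-tips or forceps hurt less, so no size is attached to it.
- **Tool and numbing are not recorded.** The row labels of Table 4 are not legible in the text available, and the eCRF pages are not in the file. Non-collection cannot be claimed.
- **The main result is at risk.** TBUT is the only measure in the success criterion (SAP 2.2), and no effect on TBUT, OSDI or EDS follows from this point.

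**What to change.** **Protocol 5.2.2.** Set the expression tool and the tool-numbing policy per site, or per subject before the randomisation envelope is opened. Apply them at all four sessions in both arms. Allow departures for the subject's comfort and record each one.

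**SAP 5.6.** Tabulate tool numbing, and the tool if captured, by arm and visit beside MGX pain. Label any analysis adjusted for actual use as supportive only, because use comes after randomisation and may itself respond to treatment.

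**Sessions already given.** Only the table can help, and only where the data were captured. Otherwise the report should say that tool numbing was discretionary and given by a role able to tell the arm.

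**Cost.** About one protocol sentence, one table, and a few eCRF fields per session at most (none if they exist). Operators lose a little flexibility. Comfort departures may still differ by arm, so the change reduces the problem and makes the remainder visible, but does not remove it.

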5.2.3. Post-treatment Instructions

- At the end of each treatment visit, the study investigator or a designee will apply a sunblock protection (30-50 SPF) to the treated area.
- On the night following treatment, subjects should generally avoid hot water, cleanse their skin gently with tepid water, and hydrate the treated area with a suitable moisturizer, Aloe Vera gel, or any other anti-burn cream or gel. It is important to avoid mechanical damage to the treated area and it should not be rubbed, scratched or picked.
- Between treatment sessions and up to 1 month after the final treatment session, subjects will be instructed to apply a sunblock protection (30-50 SPF) on the treated area, daily. The study investigator should make sure that the subject understands the need to avoid sun exposure, especially during the first 48 h after treatment.
- If the skin remains intact, subjects will be instructed to continue using standard make-up and moisturizing routine when relevant.
- In the case an unexpected skin reaction occurs, subjects will be instructed to stop using any make-up. Subjects will be instructed to immediately contact the study investigator in any case of an adverse reaction.
- Should subjects experience bothersome pain following a study treatment, they will be instructed to use an over-the-counter acetaminophen-based analgesics for pain management.

5.2.4.Check-up call

One day after Tx1, the study investigator or designee will call the subject to ask about his/her medical condition and whether any adverse events occurred.

QF-1044440 Rev. D Global Clinical Study Report Template GEN-0010523 Effective Date: July-2017			ive Date: July-2017
---	--	--	---------------------

5.3. Follow-up Visit

5.3.1.Schedule

There will be a single follow-up visit at 4 weeks (- 3 days, + 7 days) after the 4th treatment visit

5.3.2. Examiner

The examiner performing the follow-up procedures should be a different person than the study investigator who treated the subject.

5.3.3. General examination and report of adverse events

At the beginning of the follow-up visit, the examiner will assess and record the skin condition in the treated area. The examiner will then ask the subject if any adverse event occurred. If so, the adverse events will be recorded in the appropriate AE form. In any case of SAE, the study investigator must contact Lumenis within 24 hours, to elaborate whether the SAE is related to the device (UADE).

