Screening and baseline (BL) visit	Subjects will sign the IC form within one week of passing an informed consent process and having been provided the informed consent form (ICF). After signing the ICF, subjects will undergo the following baseline (BL) assessments, in the specified order:
	1. Three consecutive measurements of tear break-up time (TBUT) in both eyes
	 Routine ophthalmology tests in both eyes, including: biomicroscopy, best-corrected visual acuity (BCVA) and intra-ocular pressure (IOP)
	3. Ocular Surface Disease Index (OSDI), self-assessed using an OSDI questionnaire
	4. Eye dryness score (EDS), self-assessed using a visual analog scale (VAS)
	5. High resolution close-up photos of both eyes, including: the iris, lid margins and eyelashes
	6. Meibography of the upper and lower eyelids in both eyes
	7. Meibomian gland secretion (MGS) score in 15 glands of the lower eyelid in both eyes
Randomization	Eligible subjects will be randomized 1:1 to a study arm or to a control arm
	• The randomization process will adopt a blocked randomization strategy, using random block sizes of 2 and 4
	Four (4) treatment sessions, 2 weeks (-3 days, + 7 days) apart.
	Each treatment session will consist of the following procedures, in the specified order:
	 Subject's report of the daily usage (frequency and dose) of eye drops, warm compresses and lid hygiene since the previous visit
	Pre-treatment biomicroscopy with the slit lamp (observation of lid margins, eyelashes, conjunctiva)
Treatment	3. In the study arm:
schedule	Active IPL administered on the malar region (from tragus to tragus, below the lower eyelids, including the nose)
	In the control arm:
	Sham IPL administered on the same facial areas
	4. Meibomian gland expression (MGX) of the upper and lower eyelids in both eyes
	5. Post-treatment biomicroscopy with the slit lamp
	6. Self-assessment of pain/discomfort during IPL administration, using a VAS

Description: LUM-VBU-M22-IPL-17-01_Protocol - Clinical study protocol for M22 Dry Eye

Revision: C State: Released ECO No: ca-00000172 Effective Date: 19-Sep-2019

	7. Self-assessment of pain/discomfort during MGX, using a VAS
	There will be a single follow-up (FU) visit, which will occur 4 weeks (-3 days, + 7 days) after the final treatment session. Subjects will undergo the following assessments, in the specified order:
	 Subject's report of the daily usage (frequency and dose) of eye drop, warm compresses and lid hygiene since the previous visit

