3.3.3. Follow Up visit

There will be a single follow-up visit at 4 weeks after the final treatment session. The subject can advance the follow-up visit session by up to 3 days, or delay the follow-up visit by up to 7 days. At the beginning of the follow-up visit, the subject will self-evaluate his/her symptoms using two tools: (1) the OSDI questionnaire; (2) the EDS score using a VAS.

The following assessments will be performed in both eyes by a masked examiner:

:

• Three consecutive readings of TBUT (before any other test)

Revision: C State: Released ECO No: ca-00000172 Effective Date: 19-Sep-2019

- Routine ophthalmology tests, including:
 - Biomicroscopy with the slit lamp
 - BCVA with an ETDRS chart
 - IOP measurement
- •
- Meibography
- Meibomian gland secretion score (MGS), using the method described by Lane and colleagues. [29]
- Capture of high-resolution photos of the upper and lower eyelids, including lid margins, irises and eyelashes

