5.3.5. Assessment of TBUT

TBUT will be measured for each eye separately as follows:

- A FUL-GLO[®] fluorescein sodium ophthalmic strip (0.6 mg) will be applied to the inferior tarsal conjunctiva
- The subject will be asked to blink a few times to distribute the dye over the ocular surface.
- Once positioned at the slit lamp, the subject will close his/her eye completely.
- Then, the subject will be asked to open his/her eye without blinking.
- The timer will start as soon as the subject opens his/her eye, and it will be stopped at the first sign of tear film break of dry spot formation (first dark spot or discontinuity in the precorneal fluorescein-stained tear layer).
- For each eye, 3 consecutive readings will be taken
- TBUT will be calculated as the average of these 3 readings.

The *change* of TBUT, from baseline to the follow-up, will be used as the primary efficiency endpoint.

QF-1044440 Rev. D Glo	obal Clinical Study Report Template	GEN-0010523	Effective Date: July-2017
-----------------------	-------------------------------------	-------------	---------------------------

Revision: C State: Released ECO No: ca-00000172 Effective Date: 19-Sep-2019

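### The protocol and SAP give conflicting assessment orders at baseline and follow-up, and one of them exposes the TBUT reader to avoidable allocation cues

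*Protocol*

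**What the plan says.** **Follow-up, Protocol 5.3.** Section 5.3.2 separates the examiner from the treater: "The examiner performing the follow-up procedures should be a different person than the study investigator who treated the subject". Section 5.3.3 begins "At the beginning of the follow-up visit, the examiner will assess and record the skin condition in the treated area" and continues "The examiner will then ask the subject if any adverse event occurred". Section 5.3.4 then requires symptoms to be scored before any eye examination or outcome assessment, and gives reduction of bias as the reason. In 5.3.5 the TBUT timer is started by hand, and "it will be stopped at the first sign of tear film break of dry spot formation".

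**Follow-up, Protocol 3.3.3.** The visit opens differently: "At the beginning of the follow-up visit, the subject will self-evaluate his/her symptoms using two tools", namely OSDI and EDS. Next, "The following assessments will be performed in both eyes by a masked examiner", and the first item listed is "Three consecutive readings of TBUT (before any other test".

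**Follow-up, both synopses.** These give a numbered sequence and say that it is to be followed. It starts with the subject's "report of the daily usage (frequency and dose) of eye drop, warm compresses and lid hygiene since the previous visit", then TBUT, then routine tests, and only then OSDI and EDS.

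**Follow-up, Protocol Table 3.** OSDI and EDS come first. The tests that follow are assigned to the study investigator and listed with routine tests ahead of TBUT.

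**Baseline.** Protocol 3.3.1 and 5.1 put OSDI and EDS first, then TBUT ahead of the examiner's other tests. Section 5.1.5 again requires symptoms first, to limit bias. Both synopses put TBUT and routine tests before OSDI and EDS.

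**Masking.** Protocol 3.9 and SAP 2.8 promise every effort to mask the examiners of primary outcomes, and admit that masking cannot be complete.

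**The concern.** Two things are at stake.

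- **A single procedure.** The only efficacy visit has several versions of its sequence. OSDI, EDS and TBUT are all analysed as changes from baseline, so the order should be the same at both visits and at every site.
- **Masking of the primary reading.** TBUT ends when a person sees the first break in the tear film, so it depends on judgement. Under 5.3.3 the examiner looks at the treated skin and hears the subject's account of adverse events first. Protocol 3.8 says that masking of subjects cannot be ensured and that the sham transmits no light. Answers or skin findings may therefore point to the allocation in some subjects just before the primary reading.

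**Working it through.** No planned figure is in dispute, so the check is a comparison of texts.

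**Follow-up visit**

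| Source | Order |
|---|---|
| Protocol 5.3.3, read on through 5.3.5 | skin check → adverse-event questions → OSDI/EDS → TBUT |
| Protocol 3.3.3 | OSDI/EDS → TBUT → other eye tests |
| Protocol and SAP synopses | usage report → TBUT → routine tests → OSDI → EDS |
| Protocol Table 3 | OSDI/EDS → then a list: routine tests, TBUT, photos |

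**Baseline visit**

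| Source | Order |
|---|---|
| Protocol 3.3.1 and 5.1 | OSDI/EDS → TBUT → other eye tests |
| Protocol and SAP synopses | TBUT → routine tests → OSDI → EDS |
| Protocol Table 3 | OSDI/EDS → then a list: routine tests, TBUT, MGS, photos |

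**Comparing the orders**

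1. *5.3.3 against 3.3.3.* Both assign the start of the visit to a different step. Taken literally, both cannot be followed.
2. *Synopses against 5.3.4.* TBUT is item 2, OSDI item 4 and EDS item 5. Section 5.3.4 requires symptoms before any eye examination. This is the most direct conflict of the set.
3. *Table 3.* It is explicit only that OSDI and EDS precede the tests, which also conflicts with the synopses. Its list of tests is not clearly a sequence, so routine tests standing before TBUT is an ambiguity.
4. *Baseline.* The synopses conflict with 3.3.1, 5.1 and 5.1.5 in the same way. Correcting follow-up alone would leave the synopses with symptoms after TBUT at baseline and before it at follow-up.

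**The masking chain**

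5. Section 5.3.2 gives the follow-up procedures to the examiner. Section 5.3.3 has the examiner inspect and question, and 5.3.5 describes TBUT within the same visit. That one person does all three is the natural reading, but an inference.
6. Possible cues: anticipated adverse events include skin reactions (8.1.5). Longer-term skin response is documented at the visit after each treatment (5.2.2), which after treatment 4 is the follow-up visit, so a reaction that has cleared may still be reported. Protocol 8.3.2 also lists better skin appearance in the treated area as a known benefit of IPL.
7. Limits on those cues: longer-term reactions should go within several days (5.2.2), and the rarer complications within a few days (8.3.1). Follow-up is four weeks after the last treatment. The treated area reaches to about 2 mm from the lower lid margin (2.5.7), so nearby skin is visible at the slit lamp in any order. A subject may speak at any time.

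**The case against.** The case against is partly right.

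- **5.3.3 and 3.3.3 can be largely reconciled.** The priority given to TBUT in 3.3.3 heads a list of eye assessments, and a skin check or an adverse-event question is not an eye test. Section 5.3 then reads smoothly in sequence. This stands as a reading, but it is exactly the order that puts the cues before TBUT, and the two claims to the start of the visit remain.
- **5.3.3 might be thought to contradict 5.3.4.** It does not: 5.3.4 concerns eye examinations and outcome assessments. The synopses are what contradict 5.3.4.
- **Table 3 might be taken to mean that the treating investigator reads TBUT.** The documents do not support this, given 3.9 and 5.3.2. The term is loose wording.
- **Safety intake should come early.** This stands. Anticipated events include iritis, uveitis and photophobia (8.1.5), and Protocol 8.1 puts subject welfare first. If the questions wait until after TBUT, the examiner learns of such an event only after fluorescein and slit-lamp work. The fix must allow for that.
- **The usage report might be suspected as a cue.** Nothing in the documents shows that eye-drop, compress or lid-hygiene use reveals allocation. It need not move.
- **Incomplete masking is already disclosed.** True, but an admitted limit does not justify a cue that re-ordering can avoid.

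**Conclusion.** The conflict is real and in current text at both visits. The clearest part is the synopses against 5.1.5 and 5.3.4. The part that bears on the primary endpoint is 5.3.3 against 3.3.3. The masking consequence rests on two assumptions: that one examiner does the skin check, the questions and TBUT, and that some subjects' skin or answers reveal their arm.

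A reader might infer that the 5.3.3 order biases the primary result towards IPL, or inflates the false-positive rate by a stated amount. The documents do not support that. They give no reading error, no share of subjects affected and no direction, so any such rate would only restate what was assumed. Given the limits in step 7 and the admission in 3.9, the added bias is probably modest. Sample size, power and alpha are untouched. This is a cheap improvement, not a flaw that invalidates the design.

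**What to change.** State one order for **both** visits in Protocol 3.3.1, 3.3.3, 5.1, 5.3 and Table 3, and in the protocol and SAP synopses: OSDI and EDS first, then TBUT by the masked examiner before the other eye tests. In Table 3, name the masked examiner as the person who does the tests. The usage report can stay where it is.

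At follow-up, keep skin and adverse-event information from the TBUT reader until TBUT is recorded, in one of two ways:

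- existing site staff other than the TBUT reader collect it at the start of the visit; or
- the examiner collects it after TBUT.

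The sponsor should choose with the safety intake in mind. Either way it is collected at the same visit, so the 24-hour contact rule for serious events in 5.3.3 is unaffected.

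**Cost.** Rewording and re-ordering, with no added staff, visit or procedure. Downsides:

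- Collecting adverse events after TBUT delays the examiner's knowledge of an ocular event until fluorescein and slit-lamp work is done.
- A skin check left until after lid eversion and gland expression may show transient redness.
- A mid-study change mixes orders across subjects, so record which order each subject had.
- The risk of unmasking is reduced, not removed.
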